2.1 Primary Objectives

Primary objectives	Endpoint Description
Part A	

To examine the effect of food on the single dose PK of plixorafenib administered with cobicistat.	
Plasma PK parameters of plixorafenib (AUC_{0-t}, $AUC_{0-\infty}$, C_{\max},

	T_{\max} , K_{el} , $t_{1/2}$, CL/F , V_d/F , λ_z , and T_{lag}).

 To examine the effect of cobicistat administration on the single dose PK of plixorafenib. 	
 Urine PK parameters of plixorafenib (A_e, and $100 \cdot A_e / \text{Dose}$).

 To determine the safety of plixorafenib administered alone and with cobicistat in a single dose regimen in healthy participants. 	
 Adverse Events (AEs), clinical laboratory test results (hematology, serum chemistry, and urinalysis), vital sign measurements, 12 lead Electrocardiogram (ECG) results, and physical examination findings.
Part B	

 To examine the effect of a high-fat and a low-fat meal versus fasted state on the single dose PK of plixorafenib administered alone. To examine the effect of a low-fat meal versus fasted state on the single dose PK of plixorafenib administered with cobicistat. 	
 Plasma PK parameters of plixorafenib (AUC_{0-t}, $AUC_{0-\infty}$, C_{\max}, T_{\max}, K_{el}, $t_{1/2}$, CL/F, V_d/F, λ_z, and T_{lag}).

 To determine the safety of plixorafenib administered alone or with cobicistat (low-fat meal only) in a single dose regimen. 	
 Adverse Events (AEs), clinical laboratory test results (hematology, serum chemistry, and urinalysis), vital sign measurements, 12 lead Electrocardiogram (ECG) results, and physical examination findings.

2.2 Secondary Objectives

Secondary objectives	Endpoint Description
Part A	

 To characterize metabolites of plixorafenib in plasma and urine. 	
 Evaluation of the metabolic profile of plixorafenib in plasma and urine

To characterize the urinary excretion of plixorafenib.	
Urine PK parameters of plixorafenib (Ae, and 100*Ae/Dose).
--	--

2.3 Exploratory Objectives

Part A

- To examine the possible effect of pharmacogenomic variations on the PK of plixorafenib and/or the effect of cobicistat, including polymorphisms in P-glycoprotein (P-gp), breast cancer resistant protein (BCRP), and uridine diphosphate-glucuronosyltransferases (UGT).

Part B

- To examine the possible effects of pharmacogenomic variations on the PK of plixorafenib and/or the effect of cobicistat, including polymorphisms in P-gp, BCRP, and UGT.
- The effect of single dose administration of plixorafenib on endogenous biomarkers such as coproporphyrin may be evaluated.

3. Study Design

Schedules of assessments can be found in [Section 13](#).

This is a Phase 1, open-label, 2-part, single-dose, crossover, single-center study.

3.1. Part A

Part A is an open-label, randomized, single-dose, 3-treatment, 3-period, crossover study designed to assess the effect of food and cobicistat administration on the PK and safety of plixorafenib in 12 healthy adult participants.

Part A will consist of a screening period, one check-in, three treatment periods (with a 7-day washout between dosing in each period), and an end of study (EOS) visit as illustrated in Table 3-1:

Table 3-1 Study Description for Part A

Treatment Period	Screening	Check-in	Dosing	Confinement
1	Day -28 to -1	Day -1	Day 1	Day -1 to Day 19 (EOS)
2	N/A	N/A	Day 8	
3	N/A	N/A	Day 15	

N/A = Not Applicable, EOS = End of Study.

There will be a 7-day washout between dosing in each treatment period.

EOS visit will be conducted on Day 19.

A screening evaluation will be performed to determine each participant's eligibility for the study approximately 28 to 1 days before the first dose. Participants eligible for participation will report to the study facility 1 day before dosing in treatment period 1 for check-in.

Participants will be randomized to 1 of 6 treatment sequences at a 1:1:1:1:1:1 ratio.

Table 3-2 Treatment Sequences for Part A

Treatment Sequence Number	Treatment Sequence*	Treatment Period 1	Treatment Period 2	Treatment Period 3
1	1:2:3	900 mg plixorafenib (Fasted)	900 mg plixorafenib + 150 mg cobicistat (Fasted)	900 mg plixorafenib + 150 mg cobicistat (Fed)
2	2:3:1	900 mg plixorafenib + 150 mg cobicistat (Fasted)	900 mg plixorafenib + 150 mg cobicistat (Fed)	900 mg plixorafenib (Fasted)
3	3:2:1	900 mg plixorafenib + 150 mg cobicistat (Fed)	900 mg plixorafenib + 150 mg cobicistat (Fasted)	900 mg plixorafenib (Fasted)
4	2:1:3	900 mg plixorafenib + 150 mg cobicistat (Fasted)	900 mg plixorafenib (Fasted)	900 mg plixorafenib + 150 mg cobicistat (Fed)
5	3:1:2	900 mg plixorafenib + 150 mg cobicistat (Fed)	900 mg plixorafenib (Fasted)	900 mg plixorafenib + 150 mg cobicistat (Fasted)
6	1:3:2	900 mg plixorafenib (Fasted)	900 mg plixorafenib + 150 mg cobicistat (Fed)	900 mg plixorafenib + 150 mg cobicistat (Fasted)

*Treatment: 1 = 900 mg plixorafenib administered after overnight fast (fasted state), 2=900 mg plixorafenib + 150 mg cobicistat administered after overnight fast (fasted state), 3=900 mg plixorafenib + 150 mg cobicistat administered following a high fat, high caloric meal (fed state).

All participants will fast overnight for at least 10 hours prior to treatment. When receiving fasted treatments [900 mg plixorafenib, or 900 mg plixorafenib + 150 mg cobicistat (Fasted)], participants will continue to fast for at least 4 hours after dosing. When receiving the 'fed' treatment [900 mg plixorafenib + 150 mg cobicistat (Fed)], participants will receive a high caloric meal prior to dosing. Participants must consume the entire meal within 30 min of serving; the percentage of meal consumed will be documented. Dosing must occur 30 min (\pm 5 min) after the start of the meal. Participants receiving 'fed' treatment will receive their next meal no less than 4 hours after dosing.

Participants will remain at the facility from check in (Day -1) to EOS and would be able to leave the facility upon satisfactory safety review. Participants will be discharged from the study on Day 19 (Treatment Period 3).

The duration of the study for each participant, excluding screening period, will be approximately 20 days. Including screening period, the total study duration for each participant will be 48 days.

3.2. Part B

Part B is an open-label, randomized, single dose, 4-treatment, 3-period, crossover study designed to assess the effect of food (either a high-fat meal or a low-fat meal) on the PK and safety of plixorafenib administered alone or with cobicistat (low-fat meal only) in 16 healthy adult participants.

Part B will consist of a screening period, 1 check-in, 3 treatment periods (with a 7-day washout between dosing in each period), and an EOS visit as illustrated in Table 3-:

Table 3-3 Study Description for Part B

Treatment Period	Screening	Check-in	Dosing	Confinement
1	Day -28 to -1	Day -1	Day 1	Day -1 to Day 19 (EOS)
2	N/A	N/A	Day 8	
3	N/A	N/A	Day 15	

N/A, not applicable; EOS, end of study.

There will be a 7-day washout between dosing in each treatment period. EOS visit will be conducted on Day 19.

A screening evaluation will be performed to determine each participant's eligibility for the study approximately 28 to 1 days before the first dose. Participants eligible for participation will report to the study facility 1 day before dosing in Treatment Period 1 for check-in.

Participants will be randomized to 1 of 4 treatment sequences at a 1:1:1:1 ratio.

Table 3-4 Treatment Sequences for Part B

Treatment Sequence Number	Treatment Sequence*	Treatment Period 1	Treatment Period 2	Treatment Period 3
1	A:C:D	900 mg plixorafenib (Fasted)	900 mg plixorafenib (Low Fat Meal)	900 mg plixorafenib + 150 mg cobicistat (Low Fat Meal)
2	B:D:A	900 mg plixorafenib (High Fat Meal)	900 mg plixorafenib + 150 mg cobicistat (Low Fat Meal)	900 mg plixorafenib (Fasted)
3	D:B:C	900 mg plixorafenib + 150 mg cobicistat (Low Fat Meal)	900 mg plixorafenib (High Fat Meal)	900 mg plixorafenib (Low Fat Meal)
4	C:A:B	900 mg plixorafenib (Low Fat Meal)	900 mg plixorafenib (Fasted)	900 mg plixorafenib (High Fat Meal)

* Treatment A: 900 mg plixorafenib administered after overnight fast (fasted state), Treatment B: 900 mg plixorafenib administered following a high-fat high caloric meal (fed state-high fat meal), Treatment C: 900 mg plixorafenib administered following a low-fat meal (fed state-low-fat meal), Treatment D: 900 mg plixorafenib administered with 150 mg cobicistat following a low-fat meal (fed state-low-fat meal).

All participants will fast overnight (nothing to eat or drink except water) for at least 10 hours.

- Participants receiving fasted treatment (900 mg plixorafenib administered after overnight fast) will continue to fast for at least 4 hours after dosing.
- Participants receiving a ‘high fat’ treatment (900 mg plixorafenib administered following a high-fat high caloric meal) will receive a high fat ($\geq 50\%$ of the total caloric content of the meal), high caloric meal (approximately 800 to 1000 calories) for breakfast before dosing and this meal should derive approximately 150, 250, and 500 to 600 calories from protein, carbohydrate, and fat, respectively.
- Participants receiving a ‘low fat’ treatment (either 900 mg plixorafenib administered following a low-fat meal, or, 900 mg plixorafenib administered with 150 mg cobicistat following a low-fat meal) will receive a low-fat meal (approximately 400 to 500 total calories, with 25% of the total caloric content of the meal from fat) for breakfast before dosing.

Participants on ‘high fat’ or ‘low fat’ treatment must consume the entire meal within 30 min of serving; the percentage of meal consumed will be documented. Dosing must occur 30 min (± 5 min) after the start of the meal. Participants receiving ‘high fat’ or ‘low fat’ treatment will receive their next meal no less than 4 hours after dosing.

Participants will remain at the facility from check in (Day -1) to EOS and would be able to leave the facility upon satisfactory safety review by the investigator. Participants will be discharged from the study on Day 19 (Treatment Period 3).

The duration of the study for each participant, excluding screening period, will be approximately 20 days. Including screening period, the total study duration for each participant will be 48 days.

4. General Statistical Considerations

All statistical analyses will be conducted using statistical analysis system SAS® Version 9.4 or higher (SAS Institute, Cary, NC).

Descriptive statistics for continuous variables will include number of participants, mean, standard deviation (SD), median, minimum, and maximum, unless otherwise noted. For categorical variables, frequencies and percentages will be presented.

All tables, listings, and figures (TLFs) will be presented by part, and where applicable either; overall, or by treatment, or by treatment and overall, or by treatment sequence.

When presented by treatment, the treatments below will be used for presentations:

- Part A:
 - 900 mg plixorafenib (Fasted)
 - 900 mg plixorafenib + 150 mg cobicistat (Fasted)
 - 900 mg plixorafenib + 150 mg cobicistat (Fed)
- Part B:
 - 900 mg plixorafenib (Fasted)
 - 900 mg plixorafenib (High Fat)
 - 900 mg plixorafenib (Low Fat)
 - 900 mg plixorafenib + 150 mg cobicistat (Low Fat)

In addition to analysis by Part A and Part B, pooled analysis by treatment may be conducted as exploratory analysis.

All data listings will be sorted by participant number and collection date where applicable.

No algorithm for imputation of missing data will be employed.

For Part A and B, study days are calculated with respect to the first dose date of any study drug as below:

- If the assessment/observation date is on or after the first dose date of any study drug, then
Study Day = Assessment/Observation Date – First Dose Date of any study drug + 1;
- Otherwise,
Study Day = Assessment/Observation Date – First Dose Date of any study drug.

Unless stated otherwise, for safety analysis in Part A and B, baseline will be defined as the last non-missing assessment (including repeat and unscheduled assessments) pre-dose for each period. This may include a post-dose assessment for the previous period (for example, Day 4 assessment of Treatment Period 1 may be considered a baseline assessment for Treatment Period

2 when a subject has no pre-dose assessments for period 2). Unless stated otherwise, baseline for analysis by sequence is defined as the last assessed value prior to dosing on Day 1 of Period 1.

For summaries of safety assessments, if there are repeated measurements at a time point, the first non-missing assessment at that time point will be used in the summary tables.

For summaries of safety assessments, the maximum and minimum postbaseline result (where applicable), will be selected as the highest and lowest result (respectively) collected after baseline, including repeated and unscheduled assessments.

Unscheduled results will not be included in the summary tables by visit, except for determining Baseline or postbaseline minimum and maximum, but will be presented in data listings.

For Part A and B, to compare the post baseline results of the same treatment across different treatment periods, summaries by treatment and timepoint will standardize the visits as follows:

Analysis Visit	Recorded Visit
Baseline	Baseline result as defined above
Day 2	Day 2, Day 9, or Day 16
Day 3	Day 3, Day 10, or Day 17
Day 4	Day 4, Day 11, or Day 18
Day 5	Day 5, Day 12, or Day 19/EOS

The methodology and data handling specifications for PK data will be described in a separate analysis document created by the sponsor, *Fore Biotherapeutics*, or their designee. Any PK data needed for analysis, such as for derivations of analysis sets (see [Section 4.3](#)), will be received from the sponsor, *Fore Biotherapeutics*, or their designee.

4.1. Sample Size

The number of participants is based on clinical and practical considerations and not on a formal statistical power calculation. The total sample size of 12 participants in Part A and 16 participants in Part B is considered sufficient for the objectives of the study.

4.2. Randomization and Blinding

This is an open-label study, as such, no considerations for blinding are required.

In Part A, participants who meet all inclusion and none of the exclusion criteria will be randomly assigned to one of the 6 treatment sequences as described in [Section 3.1](#). Randomization

numbers (in sequential order) will be assigned before the first dose of study drug is administered. There will be no stratification.

In Part B, participants who meet all inclusion and none of the exclusion criteria will be randomly assigned to one of the 4 treatment sequences as described in [Section 3.2](#). Randomization numbers (in sequential order) will be assigned before the first dose of study drug is administered. There will be no stratification.

4.3. Analysis Sets

Part A and Part B

The safety set will include all participants who received at least 1 dose of plixorafenib.

The PK population will include participants who receive at least 1 dose of plixorafenib and have sufficient concentration data to support accurate estimation of at least 1 PK parameter. Participants who experience vomiting within 2 times the median T_{max} after study drug dosing will be excluded from the PK analysis.

For Part A, all enrolled participants may be used for analysis. This set will include all participants who, according to the study investigator on the electronic case report form (eCRF), had met all eligibility criteria and were ready for randomization, regardless of whether they were then randomized or not.

5. Participant Disposition

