**Table 3-1 Study Description for Part A**

Treatment Period	Screening	Check-in	Dosing	Confinement
1	Day -28 to -1	Day -1	Day 1	Day -1 to Day 19 (EOS)
2	N/A	N/A	Day 8	
3	N/A	N/A	Day 15	

N/A, not applicable; EOS, end of study

There will be a 7-day washout between dosing in each treatment period.

EOS visit will be conducted on Day 19.

A screening evaluation will be performed to determine each participant's eligibility for the study approximately 28 to 1 days before the first dose. Participants eligible for participation will report to the study facility 1 day before dosing in Treatment Period 1 for check-in.

On Day 1 of Treatment Period 1, eligible participants will be randomized to 1 of 6 treatment sequences: 1:2:3, 2:3:1, 3:2:1, 2:1:3, 3:1:2, 1:3:2. On the first day of each treatment period, each participant will receive one of the following treatments according to the sequence in which he or she is randomized:

- Treatment 1: 900 mg plixorafenib administered after overnight fast (fasted state).
- Treatment 2: 900 mg plixorafenib + 150 mg cobicistat administered after overnight fast (fasted state).
- Treatment 3: 900 mg plixorafenib + 150 mg cobicistat administered following a high fat, high caloric meal (fed state).

For Treatment 2 and Treatment 3, plixorafenib and cobicistat will be co-administered.

All participants will fast overnight (nothing to eat or drink except water) for at least 10 hours. Participants receiving Treatments 1 and 2 (fasted condition) will continue to fast for at least 4 hours after dosing.

Participants receiving Treatment 3 will receive a standard high fat ( $\geq 50\%$  of the total caloric content of the meal), high caloric meal (approximately 800 to 1000 calories) for breakfast before dosing and this meal should derive approximately 150, 250, and 500 to 600 calories from protein, carbohydrate, and fat, respectively (DHHS 2022). Participants must consume the entire meal within 30 minutes of serving; the percentage of meal consumed will be documented. Dosing must occur 30 minutes ( $\pm 5$  minutes) after the start of the meal. Participants receiving Treatment 3 will receive their next meal no less than 4 hours after dosing.

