### **7.2 ANALYSIS SETS**

The analysis populations are as follows:

- The PK population will include participants who receive at least 1 dose of plixorafenib with or without cobicistat and have sufficient concentration data to support accurate estimation of at least 1 PK parameter. Participants who experience vomiting within 2 times the median  $T_{\max}$  after study drug dosing will be excluded from the PK analysis.
- The safety population will include all participants who receive at least 1 dose plixorafenib with or without cobicistat.

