### **7.3 STATISTICAL ANALYSIS**

Details of all statistical analyses will be described in a statistical analysis plan. All data collected will be presented in data listings. Data from participants excluded from an analysis population will be presented in the data listings, but not included in the calculation of summary statistics.

For categorical variables, frequencies and percentages will be presented. Continuous variables will be summarized using descriptive statistics (number of participants, mean, median, SD, minimum, and maximum).

Baseline demographic and background variables will be summarized overall for all participants. The number of participants who enroll in the study and the number and percentage of participants who complete the study will be presented. Frequency and percentage of participants who withdraw or discontinue from the study, and the reason for withdrawal or discontinuation, will also be summarized.

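### One vomiting episode removes a participant's whole PK record, which discards usable profiles from other periods and modestly widens contrasts the vomiting did not touch

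*SAP*

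**What the plan says.** SAP 4.3 admits to the PK population dosed participants who "have sufficient concentration data to support accurate estimation of at least 1 PK parameter". It then adds: "Participants who experience vomiting within 2 times the median T_{max} after study drug dosing will be excluded from the PK analysis". Protocol 7.2 and the synopsis carry the same exclusion ("after study drug dosing will be excluded from the PK analysis"). The unit is the participant, and no section confines the exclusion to a period, treatment or profile.

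Protocol 7.3 gives the consequence: "Data from participants excluded from an analysis population will be presented in the data listings, but not included in the calculation of summary statistics". The exclusion therefore reaches the descriptive PK summaries as well as the mixed model, which Protocol 7.3.1 makes conditional on being warranted. That model has treatment as a fixed and participant as a random effect, on log AUC and log Cmax, with 90% CIs read against 80% to 125%.

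On size, SAP 4.1 says: "The total sample size of 12 participants in Part A and 16 participants in Part B is considered sufficient for the objectives of the study". The basis is practical and "not on a formal statistical power calculation". Protocol 4.4.3 allows replacement only of participants who are withdrawn or discontinued, so someone who vomits and continues is not covered.

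**The concern.** Vomiting soon after a dose compromises the profile from that dose. The documents give no reason why it should compromise profiles from other periods, whose doses are 7 days apart. The rule also sits badly with the rest of the plan. One estimable parameter is enough to enter the PK population, the model tolerates missing periods, and Part B is itself an incomplete design in which each participant receives three of the four treatments.

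At stake is precision on contrasts unrelated to the episode. In Part A, vomiting after the fed cobicistat dose would also delete that participant's two fasted periods, which carry the cobicistat comparison. In Part B, vomiting on D would delete two of A, B and C. The samples are 12 and 16, and each Part B contrast has only 8 direct pairs.

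**Working it through.** The plan states no precision or power figure to reproduce. The check compares two data sets: only the vomited profile removed, and the whole participant removed.

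**Inputs from the documents**
- Part A: "Participants will be randomized to 1 of 6 treatment sequences at a 1:1:1:1:1:1 ratio" (SAP 3.1), so 12 participants, 2 per sequence, all receiving Treatments 1, 2 and 3.
- Part B: sequences A:C:D, B:D:A, D:B:C and C:A:B, 4 participants each (Protocol 3.2, SAP 3.2). This gives 12 participants per treatment and 8 per treatment pair.
- Model: treatment fixed, participant random (Protocol 7.3.1). Period is not in the stated model, so results are given with and without it.

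**Assumptions (not in the documents)**
- Within-participant CV 30%: variance ln(1 + 0.3²) = 0.0862.
- Between-participant CV 50%: variance ln(1 + 0.5²) = 0.2231.
- Variances below are in units of the within-participant variance.

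**Profiles kept after one episode**
- Part A: 35 of 36 with period-level exclusion, 33 of 36 with participant-level exclusion.
- Part B: 47 of 48 against 45 of 48.

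**Part A, Treatment 2 versus 1, vomiting on Treatment 3**
- Without period, the variance is 2/n. Profile removed: 2/12 = 0.1667. Participant removed: 2/11 = 0.1818.
- SE ratio √(12/11) = 1.044, or +4.4%. For two vomiters √(12/10) = 1.095, or +9.5%.
- With period, one vomiter: 0.1667 to 0.1833, or +4.9%. Two vomiters: +9.5% to +11.8%, depending on sequences.

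**Part B, C versus A, vomiting on D**
- Let θ = 0.2231/(0.0862 + 3 × 0.2231) = 0.2953. With full data and no period term, the variance is 2/(12 − 4θ) = 2/10.819 = 0.1849.
- Vomiter in A:C:D: removing only D leaves 0.1849. Removing the participant gives 2/(11 − 4θ) = 2/9.819 = 0.2037. SE ratio √(0.2037/0.1849) = 1.050.
- Vomiter in B:D:A or D:B:C, by generalised least squares: 0.1860 against 0.1915, SE ratio 1.015. The loss is smaller because this participant never supplied a direct A–C pair.

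SE increase, participant-level over period-level exclusion, for Part B:

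| Vomiters on D | Without period | With period | Mean with period |
|---|---|---|---|
| 1 | +1.5% to +5.0% | +1.6% to +5.3% | +2.8% |
| 2 | +2.8% to +10.8% | +2.8% to +12.6% | +6.0% |

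The upper ends need every vomiter to be in A:C:D. The means weight equally every choice of vomiters among the 12 participants who receive D. For one vomiter the mean is (5.3 + 1.6 + 1.6)/3 = 2.8.

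**Effect on the interval**

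The 90% CI factor is exp[t(0.95, df) × √(variance × ln(1 + CV²))], here for a Part B vomiter in A:C:D, without period, at an assumed intra-participant correlation of 0.5 (variance 0.1818 against 0.2000, df 28 against 27):
- CV 20%: 1.154 to 1.163
- CV 30%: 1.237 to 1.251
- CV 40%: 1.322 to 1.341
- CV 60%: 1.495 to 1.526

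**How often**

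The chance of at least one episode over 48 independent Part B doses is 1 − (1 − p)^48. At assumed per-dose rates of 2%, 5% and 10% it is 62%, 91% and 99%.

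**The case against.** The strongest reply is that the governing text may lie elsewhere. SAP section 1 excludes PK analysis from its scope, and SAP section 4 assigns PK data handling to a separate sponsor document, which is not available here. That document may already apply the rule by profile. This stands as a limit on the claim: one cannot say that valid profiles will be lost, only that the protocol and SAP say they should be. It does not cure the wording, because a profile-level PK plan would contradict the population defined in Protocol 7.2 and SAP 4.3.

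Second, Part A is finished. SAP sections 1 and 10 report that its results were reviewed and used to design Part B. Whether anyone vomited is already known, so the Part A figures only illustrate what the rule does. This stands.

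Third, the practical effect is small. The earlier healthy-participant study, with a previous formulation, found a 3.8-fold AUC and 2.7-fold Cmax increase with cobicistat at 900 mg (Protocol 1.1.1). A 5% wider standard error would not change a no-interaction conclusion for an effect of that size. This also stands.

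A reader might infer that incomplete meals go unchecked while vomiting is punished. The documents do not support that. The meal must be eaten in full and "the percentage of meal consumed will be documented" (Protocol 3.1, with the same requirement in 3.2). A shortfall is a protocol deviation (SAP 5.2), and meal data are listed (SAP 7.2). Only a prespecified PK consequence is absent, and the PK plan may contain one. Likewise, the failure to tie median Tmax to a treatment is a missing detail to settle with the main change.

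**Conclusion.** The point holds as a modest loss of precision. As written, the rule discards usable profiles and widens contrasts that the vomiting did not affect. In Part B, one vomiter on D raises the standard error of C versus A by 1.6% to 5.3% (mean about 3%), and two raise it by 2.8% to 12.6% (mean about 6%), with period in the model. In Part A, one vomiter on Treatment 3 raises that of Treatment 2 versus 1 by 4.4% under the protocol's model and 4.9% with period added.

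These figures rest on the assumed CVs. The Part A ratios do not depend on them, and the Part B ratios depend only on the ratio of between- to within-participant variance. The vomiting rate is unknown, so the two-vomiter case is hypothetical.

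Two stronger readings fail. A fixed cost of about 5% per vomiter in Part B is true only of sequence A:C:D. Nor do the documents show that the study's conclusions are at risk: the interval factors above move by 0.009 to 0.031, and the PK plan is unseen.

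**What to change.** For Part B, replace the vomiting sentence with a period-level rule: PK parameters from a period in which the participant vomits within 2 times the median Tmax of that treatment are excluded from summaries and models, and the participant's other periods are retained in both. Use identical wording in the synopsis, Protocol 7.2, SAP 4.3 and the separate PK analysis plan.

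For Part A, which has been analysed, document any change as post hoc or report it as a sensitivity analysis.

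Optionally, add a sensitivity run that omits fed periods in which the recorded percentage of the meal eaten was below 100%.

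The cost is a small wording change in each document, including a protocol amendment that goes to the IRB (Protocol 9.2.3.2.1), plus the optional run. Numbers per treatment may become unequal, which the mixed model handles and the summary tables should show.
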